## **Withdrawal Criteria**

Investigators may withdraw a subject from the study at any time for the following reasons:

- The participant has not met the training attendance or testing session scheduling requirements of the study, as outlined above
- The participant has not met the homework requirements of the study, as outlined above
- A serious adverse event occurs
- The investigator considers, for safety reasons, it is in the best interest of the individual participant or other participants that the individual participant stop participation in the study

## **Data Security and Management**

Potential study participants' contact information including name, phone number, and email address will be recorded and accessed through a secure online application, referred hereafter as "the study app", from data contained in the existing FPHS repository protocol (described in HMS protocol #14-2691). The study app is a secure application that has been specifically created for this project to utilize as a secure, HIPAA compliant mechanism for retrieving and transferring participant information to and from the HMS data repository. Apart from recording potential participants' contact information, the study app will be used to record and access participants' responses to the HMS screening guide. The study app will additionally serve as a logistics tool to record and access information regarding a participants' study status at MSM (e.g. final screening, consent, enrollment, progress, and completion) and assigned study ID, and for the MSM team to keep the HMS team apprised of any adverse events or issues with participants. The study app is the only place where participant contact information will reside, and it will also house the study key connecting participant's identities with their study IDs.

The study app will only be accessible to designated study staff members, PI's and investigators via an online portal that requires a distinct username and password and login to a virtual private network (VPN) client. Potential participants who are deemed to be ineligible for the study will have their collected information removed from the study app within 14 days of being notified of their ineligibility.

Confidentiality of participants' records will be maintained in secure offices at the research site. Personally identifiable data (except full names and contact information as outlined above) will be stored in locked cabinets in locked rooms and/or in a password protected file on secure computer drives and study specific folder. Data will be stored in accordance with regulations required by PI and Co-I respective institutions. HIPAA laws and regulations will be implemented.

Captured data for the **Goal-Directed Resilience Training (GRIT)** study will be housed on the platform of the Research Electronic Data Capture (REDCap) on one of Morehouse School of Medicine's (MSM) research studies servers. MSM servers are positioned behind multilayered firewalls to prevent unauthorized internal or external access. Electronic data capture protocols and forms will be devised and interfaced using REDCap. Data capture, management, and use procedures and protocols at MSM are governed by the rules and policies of the Health Insurance Portability and Accountability Act (HIPAA) to protect the privacy, confidentiality and well-being of study participants. Captured data will be de-identified through assignment of study IDs to participants that are not conducive of revealing their identity. All analyses, reporting and query of the data will be conducted using participants' study IDs. Master list of linked names and identifiers to study IDs will only be accessible to designated study personnel and the study PI through the study app outlined above. Once the captured data is deposited, verified and checked for completeness, integrity and accuracy, only designated study team will have various levels-privileges to access the data for query, reporting and analyses purposes, through verifiable user's name and passwords.

Responses to enrollment questions and outcome measures that are directly administered and recorded on answer sheets will be coded and transferred onto a spreadsheet. Answer sheets and spreadsheets will not contain any identifiable information, with only the subject ID used.

When the study is closed, duplicate copies of data collected and stored by MSM will be securely transferred to HMS.

## **Risks/Assessment**

Risks and discomfort to the participant may arise from:

(1) Questions in the screening tests. The final screening assessments will consist of questions concerning possible risk for considering and pursuing suicide. The questions range from whether a participant has thought of suicide to whether they have an actual plan and intend to carry it out. They will also assess presence of disturbed thinking typical of psychosis. The questions range from another source planting thoughts in the participant's mind to the participant believing they have special powers. The Mental Health Action Plan in Appendix 8 describes our approach for assessing and keeping patients safe with regard to suicidality and psychosis.

(2) Questions from the scales during pre- and post- testing. Participants may experience the questions to be sensitive and/or unsettling. The participant may choose not to answer any questions if they do not want to. Skipping an entire test is not an option, and participants will be informed that if they choose to do this they will be withdrawn from the study. Further details are described in Appendix 8.

(3) Topics raised during the small group intervention. The interventionist will explore a subject within the training group – how the participants have experienced a subject, solved it, and how to incorporate it into the training concept and learn from it. If a participant experiences discomfort and/or

concerns that extend beyond the group's concerns and are not suitable for this approach, or a participant expresses a desire to end their participation in a given training session, the session will be ended for that individual participant and postponed until the participant feels ready to return for the next session. Incomplete sessions will be dealt with per the attendance requirements outline in the "5. Intervention Training" section above. If the participant and the trainer feel that more time is needed, therapy outside of the study training sessions may be recommended and dropping out of the study may be considered. Participants will be given referral information for outside evaluation and assistance as needed.

The Mental Health Action Plan in Appendix 8 describes our approach for assessing and keeping participants safe.

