## PROJECT DETAILS

### Experimental Design and Methods

#### Intervention Training for Former Players

Between 20 to 48 eligible and consented participants from the Atlanta area will be identified (with a goal of 40 completing the study). They will undergo a pre-training test session and will then be randomized to either the Immediate GRIT (ImT) training intervention or the Delayed Training (DeT) control. At this time there will be one intervention immediate (ImT) group and one delayed (DeT) control group of 5-12 participants per group. The immediate (ImT) group will be trained for 4 weeks with 2 biweekly sessions. At the end of GRIT training they will be post-tested. The delayed (DeT) group wait during these 4 weeks and do not receive training. At the end of the 4-week waiting period, they will also be post-tested. At this point, they will be offered GRIT training for 4 weeks with 2 biweekly sessions. At the end of their training, they will be given a second post-testing. This process will then be repeated for two additional groups of 5-12 ImT and 5-12 DeT participants.

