**Statistical Considerations**

Design. This is a balanced randomized block design. Twenty (20) to forty-eight (48) eligible and consenting participants from the Atlanta area will be identified from the cohort of research participants at the Football Players Health Study (FPHS) at Harvard University in Boston, MA. They will be selected based on answers previously given to specific FPHS survey questions listed below. They will undergo a pre-training test session and consequently be randomized with 1:1 allocation to either the Immediate GRIT training (ImT) intervention group or the Delayed (DeT) training control group. There will be two Immediate (ImT) intervention groups of 5-12 participants per training group and two Delayed training (DeT) control groups with 5-12 participants in each control group.

Outcome measures (c.f. Table 2). Sample Size and Power. This is a pilot study. Using focused pain-relevant or adaptive measures as outcomes with effect size (minimally detectable differences in weighted scores between the ImT experimental and DeT control group, scaled by pooled standard deviation) of 1, 2, 3, and 4, a regression model with treatment, age and block as effects and an overall 0.05 significance level, 20 participants per group yields an 0.80 statistical power.

For all analyses intent-to-treat principles will be adopted for those who drop out. Pre-treatment scores will be used to generate sampling frames consistent with a multiple imputation approach (Rubin, 1999) to determine post-treatment values.

Statistical Analyses. Summaries will rely on means, standard deviations for continuous variables and frequency and percentages for categorical ones. Univariate analyses for weighted scores and continuous variables groups comparisons will rely on t-tests (if normality assumptions are upheld) and/or non-parametric testing. Categorical variables will be compared using Chi-square/Fisher exact/McNamer testing. Multivariate analyses for the responses of scales/subscales weighted scores, factoring in covariates effects on interventions vs. control, age, block, pre-treatment scores, will use the Generalized Linear Mixed Modeling (GLMM) approach that will allow blocks as random effects and grant each subject their own intercept. All analyses will be conducted using SAS version 9.4

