## **2. Consenting & Pre-Testing**

Subjects will first be consented by the MSM researcher, sign a HIPAA waiver, and then undergo the final two eligibility screening assessments for suicidality and psychosis. If they qualify for the study they will then participate in the pre-testing session.

The consenting staff member will go over the consent form that describes the study, the risk and benefits, confidentiality and data security, participant rights, and each participant will have his questions answered. If the potential participant agrees with the consent information, he and the consenting person sign and date the consent form.

If a participant scores high on psychosis or suicidality during the final screening, the following steps will be initiated: They will be referred to professional mental health services as a source of support. The Georgia Crisis and Access Line ([name]) will be offered to participant for assistance. The telephone resource is available 24 hours a day/ 7 days a week and offers licensed counselors to assist. Mental Health Action Plan in Appendix 8 outlines the steps that will be taken to keep the participant safe and obtain further emergency mental health evaluation and treatment.

If deemed fully eligible to participate in the study, the participant will then begin the pre-testing session with the tests listed in Table 2. The pre-testing session will also include asking the questions included in Appendix 5. No research procedure will take place prior to the informed consent and eligibility screening. Participants will be informed that they may skip answering any questions that make them uncomfortable, but that they may not skip all questions in any one individual test and if they do, they will be withdrawn from the study.

Participants will be given sufficient time to review the consent and opportunity to ask questions. We will not be enrolling patients that cannot participate in the informed consent. Legally authorized representatives are not involved in this study. There are no medical procedures involved in this study.

The pre-testing session will last 90-120 minutes after the consent process, and will include all of the assessments noted above in the Table 2 "Outcome Measures" list.

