#### **4. Randomization**

After pre-testing of the first 10-24 participants, they will be randomly assigned to either the Immediate ImT group (n=5-12) for immediate training or to the Delayed DeT control condition (n=5-12). The method of randomization is a balanced randomized block design with 1:1 allocation to either receiving the GRIT immediate ImT training intervention or the Delayed DeT control condition. A stratified permuted block design randomization scheme will be pursued with a variable but masked block size. A one–two stratification factors will be considered for selection from position played, age, and baseline severity of pain. The randomization protocol will further dictate inspection of balance of these factors between the two groups every ten recruited participants.

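### After randomisation, the withdrawal rules do not separate skipping one test or leaving training from leaving outcome collection, which undermines the intent-to-treat commitment

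*Combined protocol and SAP*

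**What the plan says.** **Skipping a test.** Risks/Assessment, under the item headed "Questions from the scales during pre- and post- testing", rules out omitting a whole test and says that participants are to be told: "if they choose to do this they will be withdrawn from the study". Section 2 (Consenting & Pre-Testing) has the same rule for the pre-test: "they may not skip all questions in any one individual test and if they do, they will be withdrawn from the study". Both sections let a participant leave single questions unanswered.

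**Attendance and homework.** The note to Table 3 and section 5 (Intervention Training) terminate a participant from the study at the fourth missed session. Section 6 (Homework) allows withdrawal for incomplete homework.

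**Withdrawal Criteria.** This section gives investigators discretion to withdraw a participant for attendance, test scheduling or homework failures, for safety reasons, or when "A serious adverse event occurs". Skipping a whole test is not listed. Nothing here, or elsewhere in the text available, says whether outcome assessment continues after training ends.

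**Analysis.** Statistical Considerations says: "For all analyses intent-to-treat principles will be adopted for those who drop out". Post-treatment values are to be multiply imputed, and pre-treatment scores are the only imputation input named.

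**The concern.** Intent-to-treat needs outcomes from everyone randomised, whatever they did afterwards. A rule that ends study participation because one instrument was declined gives up data on the others that the participant would have supplied. A baseline-based imputation is a weaker substitute for an observed outcome. Refusing a sensitive scale may also be related to distress, and so to the outcomes, which makes the resulting missingness harder to treat as ignorable.

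The attendance and homework rules raise a further problem. They depend on behaviour during training, and until the first post-test only one arm is in training. Removing poor attenders before the main comparison would therefore thin out one arm selectively. With a target of 40 completers, a few such removals matter.

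**Working it through.** The plan gives no whole-test skip rate and no figure for withdrawal under these rules, so there is no stated result to reproduce. The nearest figure is the all-cause attrition allowance in Experimental Design and Methods: 48 − 40 = 8, and 8/48 = 16.7%.

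**Step 1: when the skip rule can reach a randomised participant.** Experimental Design and Methods says "They will undergo a pre-training test session and will then be randomized"; section 4 (Randomization) agrees: "After pre-testing of the first 10-24 participants, they will be randomly assigned". A pre-test skip therefore precedes randomisation, and only a post-test skip affects someone already allocated.
- Immediate arm: the post-test is the last scheduled visit, so what is at stake is that visit's remaining scales.
- Delayed arm: the remaining scales of the first post-test are at stake, and so are the later training and second post-test (section 7, Control Condition). The second post-test falls after the randomised comparison.

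**Step 2: which arm the training rules can reach before the first post-test.**

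| Reason for removal | Immediate arm | Delayed arm |
|---|---|---|
| Fourth missed session | Possible | Not possible: no sessions yet |
| Incomplete homework | Possible | Not possible: no homework yet |

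The documents give no rate for either, so this part is not sized.

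**Step 3: who the intent-to-treat sentence covers.** It is worded for drop-outs. Section 3 (Enrollment & Tracking) records dropouts, withdrawals and terminations as three separate categories. The plan does not say that the last two count as drop-outs for the analysis.

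**Step 4: illustrative size of the skip rule.** Table 2 lists 6 pain-relevant questionnaires, 5 adaptive ones (PACE counted once) and 3 emotional ones: m = 6 + 5 + 3 = 14. Assume each is skipped whole with probability q at the first post-test, independently. Then P(rule triggered) = 1 − (1 − q)^m.

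| m | q | Calculation | P | Of 40 |
|---|---|---|---|---|
| 14 | 0.5% | 1 − 0.995^14 | 6.8% | 2.7 |
| 14 | 1% | 1 − 0.99^14 | 13.1% | 5.2 |
| 3 (PHQ-9, GAD-7, ACE only) | 1% | 1 − 0.99^3 | 3.0% | 1.2 |

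Without the rule, each scale would be missing for only q of participants: 0.005 × 40 = 0.2 to 0.01 × 40 = 0.4 people.

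**Step 5: if testing stops at the first skip and earlier scales are kept.** The scale in position j is missing with probability 1 − (1 − q)^j. Averaged over m scales, this is 1 − (1 − q)[1 − (1 − q)^m]/(mq).
- q = 1%: 1 − 0.99 × 0.13125/0.14 = 7.2%.
- q = 0.5%: 1 − 0.995 × 0.06777/0.07 = 3.7%.

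Under these assumptions, average missingness per scale is about seven times what it would be without the rule (7.2/1 and 3.7/0.5).

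**The case against.** A reader might infer that anyone who skips a questionnaire is lost entirely and that the plan contradicts its own intent-to-treat commitment. The documents do not support that.
- Pre-test skips precede randomisation and cannot breach intent-to-treat.
- Pre-testing comes before allocation, so randomised participants have baseline scores, and imputation from those is planned.
- Nothing says that a withdrawn participant leaves the analysis or that completed scales are discarded. Withdrawal from participation can coexist with retention in the analysis set.

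A reader might also count every entry in Table 2, including the three neurocognitive batteries and the walking measure, and conclude that the rule would use up the attrition reserve: 1 − 0.99^18 = 16.5%, against 16.7%. The arithmetic is right, but the skip rate is assumed. The rule is worded for scales and questions, and the walking test is offered only as an example.

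Other objections also have force:
- Answering a single item avoids the rule.
- If skips cluster within people, fewer would trigger it than independence implies.
- Section 8 (Post-Testing) calls the post-test only nearly identical to the pre-test, so the childhood-adversity scale may not be repeated. The three-scale case would then become 1 − 0.99^2 = 2.0%.
- Risks/Assessment refers to Appendix 8 for further details, and that appendix is not in the text reviewed.
- The serious-adverse-event criterion is a safety matter unrelated to skipped tests.

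These points limit the size and the wording. They do not remove the problem: the rule is mandatory as written, it covers post-testing, and no text available keeps outcome collection going after withdrawal.

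**Conclusion.** The point holds as a weakness in stated rules, not as a strict contradiction. Followed as written, the skip, attendance and homework rules give up obtainable outcomes from randomised participants and leave them to imputation from baseline. The attendance and homework rules can act on only one arm before the main comparison.

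The skip-rule loss is unknown. About 7% to 13% for 14 questionnaires, and about 3% for the three emotional scales alone, are illustrations that rest on assumed, independent skip rates; no rate comes from the documents. The arm imbalance follows from the design itself and does not depend on those rates, though its size cannot be given. The change is worth making because it is specific and inexpensive.

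**What to change.** 1. In Risks/Assessment, state that after randomisation a skipped test is missing for that instrument only. Completed scales are kept and the remaining assessments continue.
2. In Statistical Considerations, state that withdrawn and terminated participants stay in the intent-to-treat set along with drop-outs, with missing values multiply imputed. The imputation model should include treatment arm and completed post-test scales as well as pre-treatment scores.
3. Reword the Withdrawal Criteria, and the attendance and homework passages that feed them, so that ending training does not end outcome collection unless the participant withdraws consent for it.
4. Reconcile the mandatory wording in section 2 and Risks/Assessment with the discretionary Withdrawal Criteria, which do not list skipping a test.

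The pre-test skip rule in section 2 can stay, since it acts before randomisation. Whether training stops is a clinical matter and is not addressed here.

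The cost is revised protocol and consent wording, and somewhat more instrument-level missingness for the analysis to handle.

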#### **5. Intervention Training**

There will be two Immediate Training ImT groups of 5-12 participants per training group and two Delayed Training DeT control groups with 5-12 participants in each group. One Immediate ImT intervention group will be trained at one time for 4 weeks with 2 biweekly sessions, followed by post-testing. During this time the Delayed DeT group waits, since only one group can be trained at one time. The Delayed DeT group will receive training after waiting 4 weeks and a first post testing session. At the end of its training, the DeT group will receive a second post-testing session.

Training sessions will be held at the Morehouse School of Medicine in the Research Wing. There will be two 90-minute training sessions per week, taking place between 4-6pm on two days out of Mondays through Thursdays. The exact days and times of the training will be set in advance for each group, and will not be accommodating of individual schedules.

Should a participant miss a scheduled training session or be unable to complete a session in full, the attendance requirements are as follows:

Participants are allowed to miss 2 out of 8 sessions. They are also given the option to make up one or both sessions. They are allowed to make up a maximum of 2 sessions. If they miss a 3rd session, they are not allowed to make it up but can stay in the study. If they miss a 4th session, they will be terminated from the study. The content of the makeup sessions will follow the content of the modules: (1) introduction to concepts (2) illustrative examples (3) applications to own life with exercises. Makeup sessions will be one-on-one with the interventionist, and will last no more than 30 minutes. Participants will be compensated for makeup sessions as they are for group training sessions they attend.

If a participant attends but cannot complete a training session, it will be considered a missed session if they leave before the half-way time point (45 minutes). In this case the above policy regarding missed sessions will apply. If they leave the training session after 45 minutes, they may complete the rest of the session as a homework assignment, since homework

assignments are practiced at the end of each session. Participants will only be compensated for incomplete sessions if they attend for at least half (45 minutes).

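### A training session stopped early for distress counts as a miss toward termination, and no section available for review exempts it

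*Combined protocol and SAP*

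**What the plan says.** Risks/Assessment, item (3), names topics raised in the small group as a source of discomfort. If a participant's distress goes beyond what the group can handle, or he wishes to stop, "the session will be ended for that individual participant and postponed until the participant feels ready to return for the next session". The next sentence reads: "Incomplete sessions will be dealt with per the attendance requirements outline in the" section headed 5. Intervention Training. Item (3) adds that, where more time is needed, "therapy outside of the study training sessions may be recommended and dropping out of the study may be considered", and it offers referral.

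5. Intervention Training sets the rule for partial attendance of a 90-minute session:

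- On an early exit, "it will be considered a missed session if they leave before the half-way time point (45 minutes"), and "In this case the above policy regarding missed sessions will apply".
- On a later exit, "If they leave the training session after 45 minutes, they may complete the rest of the session as a homework assignment".
- On pay, "Participants will only be compensated for incomplete sessions if they attend for at least half (45 minutes").
- On make-ups, "Participants will be compensated for makeup sessions as they are for group training sessions they attend".

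The same section, and the attendance footnote to Table 3 under Subjects, set the limits. Two of the eight sessions may be missed, and at most two may be made up. A third miss cannot be made up, but the participant may remain in the study. A fourth miss means termination. Neither place distinguishes misses by cause.

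Withdrawal Criteria uses softer wording: investigators may withdraw someone for unmet attendance, or for safety reasons.

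**The concern.** Stopping a session is the plan's own protection for a participant who becomes distressed in group training. Once the stop is referred to the attendance rule, an exit before minute 45 enters the same count as an ordinary absence, and that count ends in removal. A participant who uses the safeguard therefore moves closer to termination. If his make-ups are declined or already used, he also has a pay reason to stay until minute 45.

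The need for such an exit is foreseeable, because Module III in Table 4 asks participants to return to a painful or traumatic event. What is at stake is participant protection and continued participation. No claim is made about bias in the outcome comparison.

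**Working it through.** **Inputs.** Pay is $75 per training session for eight sessions (10. Compensation & Reimbursement). The 45-minute cut-off, the maximum of two make-ups and termination at the fourth miss come from 5. Intervention Training; the Table 3 footnote repeats the make-up and termination limits. There are four modules (Table 4) with two sessions each (6. Homework).

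**The plan's own figures.** Training pay: 8 × $75 = $600. Immediate group: $75 + $600 + $75 = $750. Delayed group: $75 + $600 + 2 × $75 = $825. All three agree with the plan.

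**The count.** Let *a* be ordinary misses and *d* distress exits before minute 45. Both enter one count, and termination comes when *a* + *d* = 4. The number of early distress exits possible without termination is therefore 3 − *a*.

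| Ordinary misses *a* | Early distress exits possible without termination |
|---|---|
| 0 | 3 |
| 1 | 2 |
| 2 | 1 |
| 3 | 0 |

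This assumes that a made-up miss stays in the count. The plan does not say so outright. The third-miss rule favours that reading, because it numbers the misses and bars a make-up for the third, which makes sense only if the first two still count after being made up. If make-ups did remove misses, two of them would move termination to the 4 + 2 = 6th miss.

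**Pay.** With *k* misses, of which *m* are made up (*m* at most 2), direct training pay lost is $75 × (*k* − *m*).

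| Misses *k* | None made up | Maximum made up |
|---|---|---|
| 1 | $75 | $0 |
| 2 | $150 | $0 |
| 3 | $225 | $75 |
| 4 (termination) | $300 | $150 |

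**Worked case.** If the modules run in order (an assumption), 4 × 2 = 8 sessions places Module III in sessions 5 and 6. Take a participant with two earlier ordinary misses, both made up with pay. He leaves session 5 before minute 45: third miss, $75 lost, he stays. He leaves session 6 before minute 45: fourth miss, a further $75 lost, and he is terminated. The direct loss is 2 × $75 = $150. With no ordinary misses, the same two exits give a count of 2, can both be made up at no loss of pay, and do not end participation.

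**The case against.** The strongest reply is that the plan chose this rule openly and that it is tolerant. Three of eight sessions may be missed for any reason without removal, and item (3) surrounds the rule with a right to stop, return when ready, referral and outside therapy. That stands, and it is why the point is minor. It does not take a distress exit out of the count.

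Three pieces of text might seem to exempt it, but do not. Item (3) speaks of postponing the session, yet its next sentence applies the attendance rule. Withdrawal Criteria gives investigators general discretion but does not mention distress, and the two attendance passages are mandatory. The general promise in 10. Compensation & Reimbursement to pay for sessions attended sits beside a specific 45-minute rule for incomplete ones.

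A reader might also infer more than the documents support:

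- **That two ordinary misses leave no room for the safeguard.** They leave one early exit, because a third miss does not end participation. Exits after minute 45 are not misses at all.
- **That the worked case costs $300, half of the $600.** That adds 2 × $75 = $150 for sessions 7 and 8, which would not be attended. The plan describes pay as repayment for time and inconvenience, so this part is pay for time not spent.
- **That Module III makes exits before minute 45 likely.** The module format described after Table 4 runs from concept to readings to personal exercises, and homework is practised at the end of each session. No timings are given, but this order suggests that the personal work comes late, when an exit is more likely to be paid and uncounted.

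Appendix 8, cited directly after item (3) for keeping participants safe, was not available. It may already contain an exemption.

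**Conclusion.** The point holds in a limited form. On the text available, a session ended for discomfort before minute 45 is a counted miss and is unpaid unless made up. It shares a four-miss termination limit with every other absence. A participant with two ordinary misses can use the safeguard once and stay; a second early use ends his participation. The direct pay loss is $75 for each early exit not made up.

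This rests on reading made-up misses as still counted and on Appendix 8 not saying otherwise. The worked case also assumes that the modules run in order. Frequency cannot be estimated from the documents.

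A reader might infer damage to the trial's results. The documents do not support that step: they give no rate for such exits and do not say whether a terminated participant is still post-tested. This is a cheap improvement of low priority.

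**What to change.** In the Table 3 footnote, 5. Intervention Training and Risks/Assessment item (3), state that a session ended under item (3) for discomfort or distress does not count toward the four-miss termination limit. The interventionist notes the session number in the study app's existing channel for adverse events and issues (Data Security and Management). The entry should not be visible to the psychiatry residents, who must test participants blind to group.

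Keep the maximum of two make-ups and their present pay, and keep the attendance rule for all other absences. Leave repeated distress exits to the safety ground in Withdrawal Criteria and to the referral route in item (3). Whether to pay for the exited session itself is optional, and for the sponsor and the IRB to decide. It would cost at most $75 per event.

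The cost is wording in three places and one short entry per event. There are two downsides. Some participants may receive less training without reaching the attendance limit. There is also a small chance of misuse, since item (3) covers a simple wish to leave as well as distress, and the two can be hard to tell apart. If Appendix 8 already exempts these exits, a cross-reference in 5. Intervention Training and Risks/Assessment is enough.
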